### 8.2.4. Statistical analysis

#### Efficacy analysis

The efficacy analysis will be executed on a modified intention-to-treat (mITT) basis.

Patient data will be included in the mITT analysis if all the four following conditions are met:

1. The patient treated a qualifying migraine.
2. The patient applied the Cefaly® Abortive Program treatment (verum or sham) during at least 30 minutes\*.
3. The headache pain severity score **AND** the migraine-associated symptom(s) at baseline were reported in the diary.
4. The headache pain severity score **OR** the migraine-associated symptom(s) at 2 hours were reported in the diary.

\*If the patient stopped the 2-hour treatment session after 30 minutes but before its end for any reason, he/she is kept in the modified intention-to-treat (mITT) analysis if all the other conditions are met.

If the patient takes anti-migraine rescue medication between 2 hours and 24 hours after the beginning of the e-TNS treatment session, the headache pain intensity and migraine-associated symptoms presence

can be affected by the medication and the last value carried forward method (2-hour value carried forward method in this case) will be applied for the 24-hour time point headache pain severity and migraine-associated symptoms.

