## 2. Study objective

The main objective of this study is to have Phase III evidences of the efficacy of the Cefaly® Abortive Program device used at home for 2 hours to treat a migraine attack, as triptans are generally used. That is to say having randomized, double-blind, sham-controlled data of the efficacy and safety of the Cefaly® Abortive Program device in the abortive treatment of acute migraine as measured by 2-hour pain freedom, pain relief and migraine-associated symptoms freedom, plus evolution of these measurements for 24 hours after the beginning of the treatment session.

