#### 4.2.3. Post-treatment phase

Starting two hours after the beginning of the treatment session, the patient is allowed to take anti-migraine rescue medication if and only if the migraine headache pain is moderate or severe, either because there has not been pain relief or because after initial pain relief (no headache or mild headache pain) a moderate or severe headache is resuming.

The patient will have to report the following data in his/her diary at 24 hours after the beginning of the treatment session (24-hour data):

- the rescue medication intake, if any, between 2 hours and 24 hours after the beginning of the treatment session, and, if applicable, the time when the medication was taken
- the headache pain severity on the following scale: 0 = no pain; 1 = mild pain; 2 = moderate pain; 3 = severe pain

- the migraine-associated symptoms (photophobia, phonophobia, nausea, vomiting)

In his/her AE reporting form, the patient will record any adverse event occurring during the 24 hours following the beginning of the treatment session and is instructed to notify the investigator immediately for any serious adverse event with the stimulation.

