## 7. Practical study modalities

### 7.1. Efficacy outcome measures

The treatment efficacy outcomes will be assessed based on the following clinical data.

- **Headache pain severity.** In order to evaluate the modification of pain severity from baseline to 2-hour and 24-hour time points, patients will be asked to note their headache pain intensity on the following scale: 0 = no pain; 1 = mild pain; 2 = moderate pain; 3 = severe pain.
- **Migraine-associated symptoms.** The patient will also note the presence of migraine-associated symptoms (photophobia, phonophobia, nausea, vomiting) and will specify which associated symptom is the most bothersome symptom (MBS) at baseline.
- **Rescue medication intake.** The patient will also record whether he/she took ANY anti-migraine rescue medication during the 24 hours following the beginning of the e-TNS treatment session.

The following table depicts when the different measures will be made:

	At baseline, i.e. just before the beginning of the e-TNS session	2 hours after the beginning of the e-TNS session	24 hours after the beginning of the e-TNS session
Headache pain severity	•	•	•
Migraine-associated symptoms	•	•	•
Identification of the most bothersome migraine-associated symptom (MBS)	•		
Rescue medication intake			•

All clinical data will be collected on a paper diary and AE reporting form.

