### 8.2.3. Statistical methods

- All relevant general, safety and efficacy data will be descriptively summarized at each time point.
- Continuous data will be summarized by the number of subjects (N), the arithmetic mean, the standard deviation, the coefficient of variation as a percentage (CV%), the median, the inter-quartile range, the minimum and the maximum value, when appropriate.
- Categorical data will be summarized by absolute (N) and relative (%) frequency tables.
- Where considered as relevant, the study data will also be graphically depicted.
- For each patient, the outcomes will be calculated according to all data available, and if necessary, imputation of missing data will be performed according to the last value carried forward method.
- Unless otherwise stated, all statistical tests will be conducted at the  $\alpha=0.05$  (2-sided) level.
- Comparison between two independent samples (verum and sham group) will be performed using either the Mann-Whitney U test (also called the Mann-Whitney-Wilcoxon (MWW), Wilcoxon rank-sum test, or Wilcoxon-Mann-Whitney test), the Fisher test or the Anova test.

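### Section 8.2.4 carries the 2-hour pain score to 24 hours for rescue users, so a compliant 2-hour responder who relapsed is summarised as pain-free or relieved at 24 hours

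*Combined protocol and SAP*

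**What the plan says.** Section 8.2.4 (Efficacy analysis) sets the 24-hour value for anyone who takes rescue between 2 and 24 hours. Because pain and symptoms "can be affected by the medication and the last value carried forward method (2-hour value carried forward method in this case) will be applied", the 24-hour entry is replaced by the 2-hour entry.

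Section 4.2.3 says when rescue may be used: from 2 hours on, "the patient is allowed to take anti-migraine rescue medication if and only if the migraine headache pain is moderate or severe". It names two routes to that state, no relief at all or the return of a moderate or severe headache after initial relief. Section 6.6 repeats the Grade 2 or 3 condition.

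Three places give the 24-hour scores a use:
- Section 2 (Study objective) lists the 2-hour measures, "plus evolution of these measurements for 24 hours after the beginning of the treatment session".
- Section 7.1 says that pain is graded "In order to evaluate the modification of pain severity from baseline to 2-hour and 24-hour time points".
- Section 8.2.3 says that "efficacy data will be descriptively summarized at each time point".

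Section 3.1 defines sustained pain freedom and sustained pain relief so that any rescue use within 24 hours is a failure.

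**The concern.** The reason given in 8.2.4 is sound as far as it goes: a score taken after medication no longer reflects the device. That justifies setting the post-rescue score aside. It does not justify replacing it with a score from before the relapse. For a 2-hour responder, taking rescue is itself evidence, under the protocol's own condition, that the headache came back at Grade 2 or 3. The replacement value says the opposite.

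At stake is the reading of the 24-hour pain results. A table of grades at 24 hours, a change from baseline, or a 24-hour pain-free or relief rate would show some known relapses as successes. A 24-hour pain-free rate could then exceed the sustained rate partly because of the imputation.

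**Working it through.** **1. The plan's own figure.** Section 8.2.1 gives 239 per group for 35.4% versus 22.0%, 90% power and 5% significance (two-sided per 8.2.3). With the pooled normal approximation, the mean rate is 0.287 and

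n = [1.960·√(2·0.287·0.713) + 1.282·√(0.354·0.646 + 0.220·0.780)]² / 0.134² = 237.4, so 238.

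That agrees with 239 to within one patient. Power at 239 is 90.2%, and 239/0.80 gives 299. Nothing below changes these figures.

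**2. The rules side by side.**

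| Pain at 2 h | Rescue, 2–24 h | Pain when rescue is taken (4.2.3, 6.6) | 24-h value under 8.2.4 | Result |
|---|---|---|---|---|
| 0 or 1 | Yes, compliant | 2 or 3 | 0 or 1 | Known relapse shown as pain-free or relieved |
| 2 or 3 | Yes | 2 or 3 | 2 or 3 | Stays a non-responder (conservative) |
| 0 or 1 | No | – | Observed score | A relapse still present at 24 h is visible |
| Any | Yes | – | Not used for sustained outcomes | Fails by definition (3.1) |

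Only the first row is wrong.

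**3. Ceilings from the home pilot (section 1).** The percentages 35.4, 60.4, 70.8, 25 and 50 all fit n = 48, as 17, 29, 34, 12 and 24 patients. Assume that the pilot's sustained outcomes were defined as in section 3.1.
- Pain-free at 2 hours but not sustained: 17 − 12 = 5. As a share of responders, 5/17 = 29.4%; of all patients, 5/48 = 10.4 points.
- Relieved at 2 hours but not sustained: 34 − 24 = 10. As a share of responders, 10/34 = 29.4%; of all patients, 10/48 = 20.8 points.

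The pilot figures do not say how many of these patients took rescue. The possible range is therefore 0 to 10.4 and 0 to 20.8 points. In an arm of 239 that is 0 to about 25 and 0 to about 50 patients.

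**4. Direction between arms (illustration).** Let r be the share of 2-hour pain-free patients who relapse and take rescue. Carrying forward adds 35.4·r(verum) points to the verum 24-hour pain-free rate and 22.0·r(sham) points to the sham rate.
- r = 10% in both arms: 3.5 and 2.2, so the arm difference rises by 1.3 points.
- r = 29.4% in both arms: 10.4 and 6.5, so it rises by 3.9 points (the ceiling if shares are equal).
- r = 10% verum, 20% sham: 3.5 and 4.4, so it falls by 0.9 points.

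The sign reverses once the sham share exceeds 35.4/22.0 = 1.61 times the verum share. The documents give neither share.

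**The case against.** The strongest reply is that no listed outcome is affected. Section 3.1 names no 24-hour pain freedom or 24-hour pain relief as such, and section 8.2.2 states no hypothesis on pain status at 24 hours. The sustained outcomes already fail every known rescue user. The relapse is not hidden either, since rescue use from 2 to 24 hours is its own secondary outcome. All of that stands and sets the limits of the point. It does not remove it: 8.2.4 writes the rule specifically for the 24-hour scores, and sections 2, 7.1 and 8.2.3 call for those scores to be reported. The sponsor's earlier sham-controlled trial, as described in section 1, reported pain-free patients at 24 hours (32% versus 13%), so such a summary is realistic here.

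It is also fair to say that the pilot figures are extreme. The ceiling requires every non-sustained responder to have taken rescue. Some may have relapsed without it, and a pain-free patient whose headache returned only to mild could not have taken rescue compliantly. This stands.

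The same sentence of 8.2.4 also carries symptoms forward. Permission for rescue depends on pain, so taking it does not show that a symptom returned, and the argument does not extend to symptoms.

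A reader might infer a second defect. Section 8.2.3 says that "if necessary, imputation of missing data will be performed according to the last value carried forward method", but the diary collects "the rescue medication intake, if any, between 2 hours and 24 hours after the beginning of the treatment session" only at 24 hours, so no earlier value exists to carry when that entry is missing. This is an unstated detail rather than a wrong rule. Diary review at the final visit (4.2.4) and Data Clarification Forms (8.1) limit how often it can arise, and the documents give no rate of missing 24-hour entries.

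**Conclusion.** The point holds for the 24-hour pain summaries. For a compliant 2-hour responder who takes rescue, the rule in 8.2.4 produces a value that sections 4.2.3 and 6.6 show to be wrong. It rests on patients following the rescue condition; someone who took rescue for mild pain need not have relapsed to Grade 2 or 3.

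The ceilings of 10.4 and 20.8 points are not estimates, and they depend on the assumed match of the pilot's sustained definition.

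Two stronger readings are not supported. One is that the rule biases the trial's efficacy result: the primary outcomes are fixed at 2 hours, before this rule applies, and the sustained outcomes exclude known rescue users by definition. The other is that the rule favours verum: this would follow only if relapse with rescue were about equally common among responders in both arms, or more common in verum, and the documents do not say so.

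**What to change.** In 8.2.4, replace the carry-forward of pain for rescue users as follows.
- In any 24-hour pain-free or pain-relief summary, count a patient who took rescue between 2 and 24 hours as not pain-free and not relieved. This matches how section 3.1 treats them in the sustained outcomes.
- In the 24-hour severity table and the change from baseline, do not carry a Grade 0 or 1 forward for these patients. Either show them as a separate category for rescue taken, or give them their baseline grade. In a qualifying attack that grade is 2 or 3, the same range as the relapse.

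This is wording only, with no new data and no change to patient management. The cost is that 24-hour rates become somewhat lower, and a patient who took rescue without a true relapse is counted as a failure, as already happens in the sustained outcomes.

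Minor note: before unblinding, state one rule for unknown rescue intake in the rescue-use and sustained outcomes, and report the opposite rule as a sensitivity analysis with the number missing per arm. Which rule is primary is the sponsor's choice. To illustrate with an assumed 5% of 2-hour responders missing, the planned 35.4% and 22.0%, and a sustained share of 12/17 in both arms: the sustained pain freedom difference is 13.4·(0.95·12/17 + 0.05) = 9.7 points if unknown rescue is read as none with pain carried forward. It is 13.4·0.95·12/17 = 9.0 points if missing counts as failure. If missing patients resemble the others, the first rule overstates the verum rate of 25.0% by 0.5 points and the second understates it by 1.2.

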#### Safety analysis

A safety analysis will be performed in case of reported adverse events comparing both groups (verum versus sham). The safety analysis will be performed on all randomized patients, i.e. patients who underwent at least the e-TNS training test session.

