- [name] conducted a multicenter, randomized, double-blind, sham-controlled trial on the acute treatment of migraine with the Cefaly® Acute device (9). One hundred and six (106) patients having a migraine attack with or without aura were randomized and included in the intention-to-treat (ITT) analysis. Among them, ninety-nine (99) were eligible for the modified intention-to-treat (mITT) analysis i.e. randomized patients having had the 1-hour stimulation treatment and having given their headache pain intensity measurement at baseline and at 1-hour time points. The last value carried-forward method was used when needed. In terms of safety, one adverse event (nausea) occurred but this event was minor and totally reversible (nausea resolved by itself after 20 minutes). There was no serious adverse events (SAE), nor were any subjective complaints or side effects reported in either group within the 24 hours after the beginning of the treatment. In terms of efficacy, in the

ITT analysis, the primary outcome, mean migraine pain intensity after the 1-hour e-TNS session compared to baseline, was very significantly more reduced in the verum group than in the sham group ( $-3.46 \pm 2.32$  versus  $-1.78 \pm 1.89$ ,  $p < 0.001$ ; or  $-59\%$  versus  $-30\%$ ,  $p < 0.001$ ). This pain relief percentage was as well significantly reduced in the verum group compared to the sham group at 2 hours and 24 hours. In the mITT analysis, mean migraine pain intensity was as well very significantly more reduced in the verum group than in the sham group at 1-hour ( $-3.83 \pm 2.13$  versus  $-1.85 \pm 1.89$ ,  $p < 0.001$ ; or  $-65\%$  versus  $-32\%$ ,  $p < 0.001$ ) and at 2-hour and 24-hour time points. In addition, the percentage of pain free patients at 24-hour time point was significantly higher in the verum group compared with the sham group (32% versus 13%,  $p < 0.05$ ), and 30% sustained pain relief for 24 hours was significantly higher in the verum group compared to the sham group (43% versus 21%,  $p < 0.05$ ). Anti-migraine rescue medication intake within the 24 hours after the beginning of the treatment was not significantly lower in the verum group.

Based on these trials providing safety and efficacy evidences for e-TNS with the Cefaly® device in the acute treatment of migraine, the Cefaly® Acute device was cleared by the FDA in September 2017 for the acute treatment of migraine with or without aura in patients 18 years and older.

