### 3. Study outcomes

#### 3.1. Efficacy outcomes

##### Primary outcomes:

1. Pain Freedom (PF) at 2 hours, defined as the percentage of patients having a reduction of a moderate or severe migraine headache (Grade 2 or 3) at baseline to no headache (Grade 0) at 2 hours after the beginning of the e-TNS session.
2. Most bothersome migraine-associated symptom (MBS) freedom at 2 hours, defined as the percentage of patients with absence, at 2 hours after the beginning of the e-TNS session, of the most bothersome migraine-associated symptom identified at baseline.

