##### Secondary outcomes:

1. Pain Relief (PR) at 2 hours, defined as the percentage of patients having a reduction of a moderate or severe migraine headache (Grade 2 or 3) at baseline to a mild headache or to no headache (Grade 1 or 0) at 2 hours after the beginning of the e-TNS session.
2. Percentage of patients with absence of photophobia, phonophobia, nausea, vomiting at 2 hours after the beginning of the e-TNS session.
3. Use of rescue medication between 2 and 24 hours, defined as the percentage of patients who took anti-migraine rescue medication between 2 and 24 hours after the beginning of the e-TNS session.
4. Sustained pain freedom at 24 hours, defined as the percentage of patients having no headache (Grade 0) at 2 hours, with no use of anti-migraine rescue medication and no relapse of headache pain within the 24 hours after the beginning of the e-TNS session.
5. Sustained pain relief at 24 hours, defined as the percentage of patients having mild or no headache (Grade 1 or 0) at 2 hours, with no use of anti-migraine rescue medication and no relapse of headache pain within the 24 hours after the beginning of the e-TNS session.

Note: The baseline corresponds to the beginning of the e-TNS session.

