#### 4.2.2. Acute treatment phase

Included patient will be instructed to treat a single qualifying migraine headache within a 2-month period following the screening visit. A migraine headache is a qualifying migraine when all the following criteria are met:

1. The migraine headache severity is moderate or severe (Grade 2 or 3).
2. The migraine headache is associated with at least one of these migraine-associated symptoms: photophobia, phonophobia, nausea, vomiting.
3. The migraine headache started less than four hours ago.
4. No other migraine headache or headache has occurred in the previous 48 hours.
5. The migraine headache is not already resolving on its own i.e. the pain is not already diminishing.
6. No anti-migraine rescue medication has been taken since the beginning of the migraine headache.

In case of qualifying migraine, patient will have to apply the Cefaly® Abortive Program device (verum or sham) for a complete treatment session of 2 hours as soon as the migraine headache is moderate or severe (Grade 2 or 3).

In his/her paper diary, the patient will have to report the following data just before the start of the e-TNS treatment session (baseline data):

- if there is any aura with the qualifying migraine attack
- the headache pain severity on the following scale: 0 = no pain; 1 = mild pain; 2 = moderate pain; 3 = severe pain

---

 if the patient woke up with a migraine, the starting time of the migraine is considered to be at the time of wake-up.

- the migraine-associated symptoms (photophobia, phonophobia, nausea, vomiting) and will specify which associated symptom is the most bothersome symptom (MBS).

Two hours after the beginning of the treatment session, whatever its duration (normally just after removing the device and the electrode if the session ran correctly for 2 hours), the patient will have to report the following data (2-hour data) in his/her diary:

- the headache pain severity on the following scale: 0 = no pain; 1 = mild pain; 2 = moderate pain; 3 = severe pain
- the migraine-associated symptoms (photophobia, phonophobia, nausea, vomiting)

Patients will be instructed NOT to take any anti-migraine rescue medication during the 2-hour treatment session. Medication intake during the 2-hour treatment phase will be considered as a protocol violation.

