## 9.4. Expected AE

The expected AEs of the Cefaly® Abortive Program device are:

- Reversible skin irritation at the place of electrode
- Allergic reaction to the gel of the electrode (1 out of 1000)
- Pain during the session
- Sleepiness
- Neck pain
- Nausea
- Tooth pain

Paraesthesia, tingling/itching and burning sensation are normal effects of the device and should therefore NOT be considered as AEs, unless this sensation leads to treatment discontinuation.

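### New nausea or vomiting recorded in the diary reaches the safety analysis only if it is also reported as an adverse event, and the planned efficacy outcome shows it only net of relief in other patients

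*Combined protocol and SAP*

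**What the plan says.** **Nausea as an expected event.** Nausea is in the list that section 9.4 opens with "The expected AEs of the Cefaly® Abortive Program device are". Vomiting is not in that list. Section 9.4 goes on to name sensations that are normally not adverse events, and nausea is not one of them. Section 1 says of the earlier sham-controlled trial that "one adverse event (nausea) occurred but this event was minor and totally reversible", "nor were any subjective complaints or side effects reported in either group within the 24 hours" after treatment began. It does not give the arm of the nausea case.

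**What the diary records.** Section 4.2.2 has the patient report at baseline "the migraine-associated symptoms (photophobia, phonophobia, nausea, vomiting) and will specify which associated symptom is the most bothersome symptom (MBS"). The same four symptoms are recorded again at 2 hours (4.2.2) and 24 hours (4.2.3), as the table in 7.1 confirms. New onset can therefore be derived for each patient.

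**How these data are analysed.** The second secondary outcome in 3.1 is "Percentage of patients with absence of photophobia, phonophobia, nausea, vomiting at 2 hours after the beginning of the e-TNS session". It is not split by baseline status. The second primary outcome concerns the absence at 2 hours "of the most bothersome migraine-associated symptom identified at baseline". Section 8.2.3 adds descriptive summaries at each time point and names no shift from baseline.

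**How safety is analysed.** Section 3.2 rests safety on the number and severity of reported adverse events. Section 8.2.4 says: "A safety analysis will be performed in case of reported adverse events comparing both groups (verum versus sham").

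**How adverse events are captured.** The patient has a separate form covering the session and the 24 hours from its start (4.2.2, 4.2.3). At the final visit (4.2.4) the investigator reviews that form and asks about effects not written on it. The diary is reviewed for completeness and accuracy.

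**The concern.** The same symptom can be recorded in two places: a diary field for migraine-associated symptoms and an adverse event form. No section says when nausea during an attack is a migraine symptom and when it is an adverse event, and no step sets the two records side by side. A patient who has marked new nausea in the diary may reasonably see no need to write it down again. The plan then makes no safety use of a structured, blinded, sham-controlled record of an effect on its own expected list, and relies on free reporting and one general question.

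The planned efficacy summary does not make up for this. The share without nausea at 2 hours adds together patients who lost the symptom and patients who never had it, and subtracts new cases without showing them. A neutral or favourable share is compatible with more new nausea on verum. At stake is how well the trial describes tolerability. Neither primary outcome nor the sample size is affected.

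**Working it through.** **1. The plan's own figure, which supplies the group size.** Section 8.2.1 gives 35.4% v 22.0%, 90% power, 5% level and 239 per group. The two-sided pooled formula is

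n = [1.960·√(2·p̄·(1−p̄)) + 1.282·√(p₁(1−p₁) + p₂(1−p₂))]² / (p₁−p₂)², with p̄ = 0.287.

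This is (1.254 + 0.811)² / 0.134² ≈ 237.4, so 238 against 239 stated. With 20% loss, 239/0.80 = 298.75, so 299 as stated. The figure reproduces and is not in dispute.

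**2. What the net outcome measures.** Take the secondary outcome symptom by symptom (an assumption; the wording does not settle it). Let b be the share with nausea at baseline, r the share of those relieved by 2 hours, and e the share of the rest who develop it.

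- Nausea-free at 2 hours = b·r + (1−b)·(1−e)
- Verum minus sham = b·Δr − (1−b)·Δe
- The difference is zero when Δe = b·Δr/(1−b)

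For a 10-point relief advantage, the excess onset fully hidden is 4.3 points at b = 30%, 10 points at b = 50% and 23.3 points at b = 70%.

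**3. Range of scenarios.** The documents give none of these rates, so all are assumed. There are 239 per arm. Sham relief is 40% and sham onset 3% throughout.

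| b | Verum relief | Verum onset | Nausea-free, sham v verum | New cases, sham v verum |
|---|---|---|---|---|
| 30% | 50% | 8% | 79.9% v 79.4% | 5.0 v 13.4 |
| 30% | 50% | 13% | 79.9% v 75.9% | 5.0 v 21.7 |
| 50% | 50% | 13% | 68.5% v 68.5% | 3.6 v 15.5 |
| 50% | 60% | 8% | 68.5% v 76.0% | 3.6 v 9.6 |
| 70% | 60% | 13% | 57.1% v 68.1% | 2.2 v 9.3 |

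Third row, worked: sham 0.5·0.40 + 0.5·0.97 = 0.685; verum 0.5·0.50 + 0.5·0.87 = 0.685. New cases are 119.5·0.03 = 3.6 and 119.5·0.13 = 15.5. The second row shows that the net share can also move against verum, so masking is possible but not certain.

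**4. The same effect in whole counts (assumed).** Take 240 per arm, half with baseline nausea. Of those 120, 60 on verum and 72 on sham still have it. Of the other 120, 12 on verum and 3 on sham develop it.

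- Net: 72/240 v 75/240 (30.0% v 31.3%), Fisher p = 0.84
- New onset: 12/120 v 3/120 (10% v 2.5%), Fisher p = 0.03

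**5. What a new-onset comparison could detect.** Exact Fisher power, two-sided 5%:

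- 10% v 2.5%: 37%, 58% and 75% with 80, 120 and 160 per arm at risk
- 5% v 2.5%, 120 per arm: 9%
- 4% v 2.5%, 120 per arm: 4%

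The comparison would be informative only for a large excess, which argues for estimates with intervals and against a test.

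**6. Two further places where diary nausea drops out (8.2.4).** Patients treated for less than 30 minutes leave the efficacy set, whatever their reason for stopping. After rescue medication, the 2-hour value replaces the 24-hour symptom value, so nausea that first appears after 2 hours in those patients is not seen in that analysis.

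**The case against.** A reader might infer that new nausea goes uncounted. The documents do not support that. The adverse event definition in 9.1 covers any unfavourable symptom whatever its cause, 9.5 has patients report all events, the form covers the full 24 hours, and the final-visit question is a second route. Anything so reported is compared by arm in the safety population. A new case also lowers its own arm's symptom-free share, because the secondary outcome is not limited to patients who had the symptom at baseline. For the same reason it is wrong to say that the diary data can only favour the device.

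A reader might also infer that nausea is an established harm of the device. The documents list it as expected and report one minor, self-resolving case among 106 randomised (0.9%), arm not stated. The open-label pilot with 30 patients analysed reported no events (section 1). Nothing shows nausea to be commoner on verum than on sham.

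The scenarios use assumed rates, and those that cancel exactly were chosen to do so. That limits what can be said about size. It leaves the mechanism intact.

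Finally, the diary review in 4.2.4 aims to avoid discrepancies, which could be stretched to include disagreement with the adverse event form. The text describes a review of the diary, followed by a separate review of the form, and names no comparison. What stands is that capture as an adverse event depends on a second report, and that no new-onset summary is named.

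**Conclusion.** The point holds in this limited form. New nausea or vomiting in the diary is not carried into the safety analysis unless it is also reported as an adverse event, nothing reconciles the two records, and the efficacy outcome counts it only net. The gap is one of capture and display. It is not evidence that the device causes nausea.

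Its size is unknown. It depends on baseline, relief and onset rates, and on how often patients enter on the form what they have already marked in the diary; the documents give none of these. Over the assumed range, the net share ran from a fall on verum, through no difference, to an apparent benefit, while new cases were always more frequent on verum by construction. Since power for realistic smaller excesses is low, a descriptive analysis is the right level. The change is worth making because it uses data already in hand, but it has no bearing on the primary conclusions.

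**What to change.** Add to the Safety analysis in 8.2.4 a descriptive table by arm:

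- **Set:** all patients who started the home treatment session and have diary data, including sessions under 30 minutes.
- **At 2 hours:** number and percentage with new nausea, and separately new vomiting, among those without that symptom at baseline, with exact 95% confidence intervals and the verum minus sham difference with its 95% interval.
- **At 24 hours:** the same, from observed diary values and not carried-forward ones, for all such patients. Display rescue use and do not exclude on it, because it arises after randomisation and may differ by arm.
- **Placement:** beside the adverse event table, whether or not the symptom was entered on the form, and labelled as not a formal test.

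In 4.2.4, have the existing final-visit review compare the diary symptom entries with the adverse event form. The plan should also state how diary symptoms relate to adverse event recording; that rule is for the sponsor and investigators to settle.

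The cost is one table from data already collected and one line in the visit instructions. The small downside is that some new nausea is the natural course of the attack, so the sham arm must be read as the reference.
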